# 21 Committees

### 21.1 Data Monitoring Committee

The Data Monitoring Committee (DMC) is responsible for the oversight review of all AEs. The DMC will include leading experts in cardiology, and biostatistics who are not participating in the study and who have no affiliation with BSC. During the course of the study, the DMC will review accumulating safety data to monitor the incidence of CEC events and other trends that would warrant modification or termination of the study. Responsibilities, qualifications, membership, and committee procedures are outlined in the DMC Charter.

Any DMC recommendations for study modification or termination because of concerns over subject safety or issues relating to data monitoring or quality control will be submitted in writing to BSC for consideration and final decision. However, if the DMC at any time determines that a potentially serious risk exists to subjects in this study, the DMC chairman will immediately notify both BSC and the Principal Investigators.

## 21.2 Clinical Events Committee

A Clinical Events Committee (CEC) is an independent group of individuals with pertinent expertise that reviews and adjudicates all treated spontaneous episodes with available source documentation, relevant AEs, and all subject deaths reported by study investigators. Relevant AEs are those deemed to be attributed to either/ both of the PGs in the mCRM Coordinated System, the S-ICD electrode, or the procedure to implant the EMPOWER PG. The CEC will review a safety event dossier for each submitted AE or death, which may include copies of subject source documents provided by study sites, BSC reserves the right to submit other AEs as well, if deemed necessary.

Committee membership will include practitioners of cardiology, as well as other experts with the necessary therapeutic and subject matter expertise to adjudicate the event categories outlined above. CEC responsibilities, qualifications, membership, and committee procedures are outlined in the CEC charter.

# 22 Suspension or Termination

### 22.1 Premature Termination of the Study

Boston Scientific reserves the right to terminate the study at any stage but intends to exercise this right only for valid scientific or business reasons and reasons related to protection of subjects. Investigators, associated IRBs/ECs/REBs, and regulatory authorities, as applicable, will be notified in writing in the event of study termination.

### 22.2 Criteria for Premature Termination of the Study

Possible reasons for premature study termination include, but are not limited to, the following.

- The occurrence of unanticipated adverse device effects that present a significant or unreasonable risk to subjects enrolled in the study.
- An enrollment rate far below expectation that prejudices the conclusion of the study.

• A decision on the part of Boston Scientific to suspend or discontinue development of the device.

### 22.3 Termination of Study Participation by the Investigator or Withdrawal of IRB/ EC/ REB Approval

Any investigator, or associated IRB/EC/REB, or regulatory authority may discontinue participation in the study or withdraw approval of the study, respectively, with suitable written notice to Boston Scientific. Investigators, associated IRBs/ECs/REBs, and regulatory authorities, as applicable, will be notified in writing in the event of these occurrences.

### 22.4 Requirements for Documentation and Subject Follow-up

In the event of premature study termination, a written statement as to why the premature termination has occurred will be provided to all participating sites by BSC. The IRB/EC/REB and regulatory authorities, as applicable, will be notified. Detailed information on how enrolled subjects will be managed thereafter will be provided.

In the event an IRB, REB or EC terminates participation in the study, participating investigators, associated IRBs/ECs/REBs, and regulatory authorities, as applicable, will be notified in writing. Detailed information on how enrolled subjects will be managed thereafter will be provided by BSC.

In the event a Principal Investigator terminates participation in the study, study responsibility will be transferred to another investigator, if possible. In the event there are no opportunities to transfer Principal Investigator responsibility; detailed information on how enrolled subjects will be managed thereafter will be provided by BSC.

The Principal Investigator or his/her designee must return all study-related documents and investigational product, including the PRM software pen drive, to BSC, unless this action would jeopardize the rights, safety, or welfare of the subjects.

### 22.5 Criteria for Suspending/ Terminating a Study Site

Boston Scientific reserves the right to stop the inclusion of subjects at a study site at any time after the study initiation visit if no subjects have been enrolled for a period beyond 3 months after site initiation, or if the site has multiple or severe protocol violations/noncompliance without justification and/or fails to follow remedial actions.

In the event of termination of site participation, all study devices and testing equipment, as applicable, will be returned to BSC unless this action would jeopardize the rights, safety or well-being of the subjects. The IRB/EC/REB and regulatory authorities, as applicable, will be notified. Study participants will be contacted, as applicable, and be informed of changes to study visit schedule.

## 23 Study Registration and Results

### 23.1 Study Registration

To comply with applicable laws and regulations, the study will be registered on a publicly accessible database.

## 23.2 Clinical Investigation Report

Study results will be made available in accordance with the legal requirements and the recognized ethical principles, in accordance with the Boston Scientific Policy. A Clinical Investigation Report will be made available to all investigators, IRB/EC/REB and regulatory authorities, as applicable in accordance with the Boston Scientific Policy and local requirements. As applicable an abbreviated Clinical Investigation Report will be made available on a publicly accessible database.

### 23.3 Publication Policy

BSC requires disclosure of its involvement as a sponsor or financial supporter in any publication or presentation relating to a BSC study or its results. BSC will submit study results for publication (regardless of study outcome) following the conclusion or termination of the study. The study results submitted will include the number of subjects that enroll into the study, as well as the number of subjects that complete the study, a summary of results for primary and secondary outcome measures, statistical analyses, and adverse events.

Boston Scientific adheres to the Contributorship Criteria set forth in the Uniform Requirements of the International Committee of Medical Journal Editors (ICMJE; http://www.icmje.org). In order to ensure the public disclosure of study results in a timely manner, while maintaining an unbiased presentation of study outcomes, BSC personnel may assist authors and investigators in publication preparation provided the following guidelines are followed:

- All authorship and contributorship requirements as described above must be followed.
- BSC involvement in the publication preparation and the BSC Publication Policy should be discussed with the Coordinating Principal Investigator(s) and/or Executive/Steering Committee at the onset of the project.
- The First and Senior authors are the primary drivers of decisions regarding publication content, review, approval, and submission.

The data, analytic methods, and study materials for this clinical trial may be made available to other researchers in accordance with the Boston Scientific Data Sharing Policy (https://www.bostonscientific.com/)

# **25** Abbreviations and Definitions

### 25.1 Abbreviations

Abbreviations are shown in Table 25-1.

Abbreviation/Acronym	Term
ADE	Adverse Device Effect
AE	Adverse Event
A/P	Anterior/ Posterior
AST	Automated Screening Tool
ATP	Anti-tachycardia Pacing
BSC	Boston Scientific
СА	Competent Authority
CEC	Clinical Events Committee
CFR (within stats sections)	Complication-free Rate
CFR	Code of Federal Regulations
CIED	Cardiac Implantable Electronic Device
CMS	Center for Medicare and Medicaid Services
CRF	Case Report Form
CRM	Cardiac Rhythm Management
DMC/ DSMB	Data Monitoring Committee/ Data and Safety Monitoring Board
DXA	Dexamethasone Acetate
EC	Ethics Committee
ECG	Electrocardiogram
EDS	Electrode Delivery System (for S-ICD)
EIT	Electrode Insertion Tools (for S-ICD)
EMPOWER MPS	EMPOWER Modular Pacing System; consists of the EMPOWER
	PG and implant delivery catheter
EMPOWER PG	EMPOWER Pulse Generator
EOS	End of Service (pertaining to EMPOWER PG battery)
ERI	Elective Replacement Indicator (pertaining to S-ICD PG battery)
Fr	French, a measurement system commonly used to measure the
	size of a catheter
FDA	Food and Drug Administration
ICD	Implantable Cardioverter Defibrillator
ICF	Informed Consent Form
IDE	Investigational Device Exemption
IRB	Institutional Review Board
ISO	International Standard Organization

#### **Table 25-1: Abbreviations**

Page 120 of 148

Table	25-1:	Abbr	eviations
-------	-------	------	-----------

Abbreviation/Acronym	Term
J	Joules
LAO	Left Anterior Oblique views
LCP	Leadless Cardiac Pacemaker
LOC	Loss of Capture
LRL	Lower Rate Limit
LVAD	Left Ventricular Assist Device
MCR	Metabolic-Chronotropic Relation
MPS	Modular Pacing System
MVT	Monomorphic Ventricular Tachycardia
P/A	Posterior/ Anterior
PCT	Pacing Capture Threshold
PG	Pulse Generator
PMDA	Pharmaceuticals and Medical Devices Agency
PMST	Paced Morphology Sensing Test
PRM	Programmer/ Recorder/ Monitor
PTM	Physician's Technical Manual
REB	Research Ethics Board
RV	Right Ventricle
SADE	Serious Adverse Device Effect
SAE	Serious Adverse Event
SAS	Statistical Analysis System
SCD	Sudden Cardiac Death
S-ECG	Subcutaneous electrocardiogram
S-ICD	Subcutaneous ICD
TSF	Technical Source Form
TV-ICD	Transvenous ICD
UADE	Unanticipated Adverse Device Effect
USADE	Unanticipated Serious Adverse Device Effect
VF	Ventricular Fibrillation
V00	Asynchronous pacing mode
VT	Ventricular Tachycardia

### 25.2 Definitions

Terms used in this protocol are defined in Table 25-2.

Term	Definition		
S-ICD System	(EMBLEM/ EMBLEM MRI) S-ICD Pulse Generator, Models A209/ A219 or future BSC S-ICD Pulse Generator + (EMBLEM) S-ICD Electrode Model 3400/3401, Model 3501 or future BSC S-ICD Electrode 		
EMPOWER MPS	EMPOWER Modular Pacing System, Model B170, which consists of the EMPOWER leadless pacemaker and the delivery catheter		
EMPOWER PG	EMPOWER Pulse Generator: the leadless pacemaker		
EMPOWER System	
 
EMPOWER MPS (EMPOWER pacemaker and Delivery Catheter) and Luer Cap (Model B170)
 
EMPOWER MPS accessories:         
 
EMPOWER Retrieval Catheter, Snare Catheter Lock, Luer Caps, and Hemostasis Valve (Model 8780)
 
EMPOWER Introducer Sheath (Model 8782)
 
EMPOWER Conducted Telemetry Cable (Model 6396)
 
EMPOWER Sterile Tray Cable (Model 6157)
 
EMPOWER Single-loop Snare (Model 8784) or EMPOWER Tri-loop Snare (Model 8785)
 
 
 
LATITUDE Programming System (Model 3300)
 
Programmer Application Software (Model 3870) and associated Programmer Firmware
 
Guidewire
 
Electrocardiogram electrodes (supplied by clinical center)
 
		
Communication Success	Any evidence of a paced beat during communication testing in a given		
	posture at the initial programmed communication Programmed Telemetry Setting		
Communication Threshold Test	This is a communication test that results in determining the minimum Telemetry Value that achieves two successful communication tests, regardless of sequence. A Communication Threshold test is required at		

<sup>46 Note that Cameron Health Q-Trak Electrode Model 3010 is the same as BSC Models 3400/3401, and is also allowable.

<sup>47 Note: Another compatible introducer sheath may be used that is not part of the EMPOWER System accessories. Refer to Table 26-1 and the EMPOWER Modular Pacing System Physician's Technical Manual and Label Supplement, as well as the EMPOWER Retrieval System Physician's Technical Manual and Label Supplement for more information.

Page 122 of 148

Table 25-2: Definitions

Term	Definition
	Implant, Pre-Discharge, and the 1-Month Follow-up in one or more postures, as described in the specific follow-up section. A Communication Threshold test is required at any other protocol- required follow-up in the event of a failed Communication Test.
Communication Test	This is a communication test that is initiated at the initial programmed Telemetry Setting. A Communication Test is required at the 6-Month, and Semi-Annual Visits, as well as any Additional Visits which are conducted due to an adverse event related to communication of the mCRM Coordinated System. Note that if the Communication Test ends in unsuccessful communication, a Communication Threshold Test is required.
Coordinated System/ mCRM Coordinated System/ mCRM Therapy System	(EMBLEM) S-ICD System + EMPOWER PG
Major complication related to EMPOWER MPS	
 
Major complications are those adverse events resulting in:
 
Death
 
Permanent loss of device function due to mechanical or electrical dysfunction of the device
 
Hospitalization
 
Prolonged Hospitalization by at least 48 hours*
 
System revision, including reposition, replacement, and explant.
 
*Hospitalization is extended by ≥48 hours beyond expected hospital discharge (from implant or hospital admission for another cause)
 

mCRM Programmable Parameters	
 
The S-ICD parameters listed below are not accessible without the PIN.
 
These parameters are all related to ATP.
 
mCRM (On/Off)
 
Number of ATP Requests in Conditional Shock Zone (0, 1, 2, 3)
 

	
 
QUICK CONVERT™ ATP in Shock Zone (On/Off)
 

	• Telemetry Setting (1, 1.5, 2, 2.5, 3, 3.5, 4, 4.5, 5, 5.5, 6, 6.5, 7)
Normal battery depletion	A pulse generator that is not associated with a complaint and has reached its elective replacement indicator(s) with implant time that meets or exceeds the nominal (50th percentile) predicted longevity at default (labeled) programmable settings OR with implant time exceeding 75% of the expected longevity using the longevity calculation tool available at time of product introduction, calculated using the device's actual use conditions and programmable settings

Page 123 of 148

Table 25-2: Definitions

Term	Definition
Permanent Loss of Device Function	Refers to: 1) the permanent loss of shock therapy and/or post shock pacing (S-ICD only); 2) permanent loss of appropriate sensing in all available sensing configurations (oversensing that results in persistent inappropriate shocks or undersensing that could lead to undetected arrhythmias) (S-ICD only). Loss of device function includes programming the PG permanently off or temporarily off in advance of an explant/revision (applies to both EMPOWER and S-ICD.
Patient/ Potential Subject	A person who is a potential candidate for the MODULAR ATP Clinical Study
Subject	A person who has been enrolled into the MODULAR ATP Clinical Study
Spontaneous episode	Any arrhythmia that is stored by the S-ICD pulse generator. For the purpose of the MODULAR ATP Clinical Study, only ventricular arrhythmias will be collected.
Time 0	Timing of study-required follow ups will be determined based on the date that the mCRM Coordinated System is implanted (successful implant of both the S-ICD System, with clinical firmware, and EMPOWER PG)
	Note: Subjects classified as a Partial Implant that are implanted with an EMPOWER PG must be followed according to this protocol, with all relevant EMPOWER PG device data and testing collected. Time 0 for the purpose of determining timing of follow ups for these subjects is the day it is determined the S-ICD will not be implanted.
Time to therapy for inductions	Time to therapy for induced episodes is defined as the interval starting 2000ms after the last induction artifact (the time of the post induction refractory) and ending at the onset of the shock deflection on the S-ECG recording.
Time to therapy for spontaneous episodes	Time to therapy for spontaneous episodes is defined as the interval starting when the cycle length of the patient's rhythm is greater or equal to the lowest programmed zone cutoff and measured until the start of delivery of ATP pulses or the shock marker.

Page 124 of	148
	_
C - NAP O WE SHO	
102931 10102931	
O DE LA LASSE AND	

MODULAR ATP	
	Page 125 of 148

MODULAR ATP	
	Page 126 of 148
	C I
	_
	I

MODULAR ATP
Page 127 of 148

MODULAR ATP	
	Page 129 of 148
	6

MODULAR ATP	
	Page 130 of 148

Page 131 of 148

Page 134 of 148

MODULAR ATP

MODULAR ATP Page 136 of 148

Page 137 of 148

MODULAR ATP

MODULAR ATP	
	Page 138 of 148

MODULAR ATP	
	Page 142 of 148

Page 144 of 148

MODULAR ATP

Page 148 of 148

MODULAR ATP

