**Table 10-9: S-ICD Programming for Primary Prevention Subjects** 

 <sup>24 Stiles, Martin K., et. al 2019 HRS/EHRA/APHRS/LAHRS focused update to 2015 expert consensus statement on optimal implantable cardioverter-defibrillator programming and testing. *Heart Rhythm* 2019;17:220–228)

<sup>26 Lower bound of the conditional shock zone should be >3x the Lower Rate Limit (LRL) of EMPOWER

S-ICD Programming for Secondary Prevention Subjects (all Recommended programming, except where noted)				
Therapy Zone	Rate	АТР		
Conditional Shock Zone	Physician Discretion 	At least 1 ATP request Required ; up to 3 acceptable (ATP scheme is per physician discretion)		
Shock Zone	Physician Discretion	Quick Convert ATP ON		

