#### 11.2 Ancillary Objectives

The following data will be collected in the MODULAR ATP Clinical Study and summarized at the time of endpoint analysis for all subjects, where applicable, and the data are available. Additional information regarding the ancillary objectives can be found in the MODULAR ATP SAP.

- Summary of the mCRM Therapy System implant procedure characteristics
  - o Initial implant success rate of the EMPOWER PG
  - o Initial implant success rate of the S-ICD (de novo Implants)
- Summary of pacing impedance and sensing amplitude at protocol-required follow ups
- Summary of ventricular tachycardia (VT)/ ventricular fibrillation (VF) conversion and sensing interaction testing
- Summary of Communication Threshold Test at Implant, Pre-Discharge, 1 Month Visit and available Semi-Annual visits
- Summary of Communication Test results at available Semi-Annual visits
- Summary of incidence and threshold for Communication Muscle Stimulation at Implant
- Summary of number of postures with a successful Communication Test at the 6 Month Visit
- Summary of EMPOWER PG PCT at protocol-required follow ups
- Summary of spontaneous treated VT/ VF episodes
- Incidence of syncope related to treated and untreated spontaneous episodes of VT/ VF above the lowest programmed rate cutoff
- Incidence and appropriateness of post-shock demand pacing by the EMPOWER PG

- Summary of Inappropriate Therapy
- Summary of Major EMPOWER MPS System- and Procedure-related Complications through both 6 and 12 months after the implant procedure
- Summary of mCRM Therapy System-related complications through both 6 and 12 months after the implant procedure\*
- Summary of the EMPOWER PG performance from Holter Monitor recording
- Summary of EMPOWER PG battery charge remaining to End of Service (EOS) at protocol-required follow ups
- Summary of S-ICD PG remaining battery to Elective Replacement Indicator (ERI) per protocol-required follow ups (baseline adjusted to time of enrollment for S-ICD PGs implanted prior to enrollment in MODULAR ATP)

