1.3 Ancillary Objectives

Additional information regarding the ancillary objectives outlined in Section 11.2 of the MODULAR ATP Clinical Study Protocol is found below:

- Summary of the mCRM Therapy System implant procedure characteristics:
 - Initial implant success rate of the EMPOWER PG Number of implants out of all attempted implants
 - Initial implant success rate of the S-ICD (De Novo Implants) Number of implants out of all attempted implants
 - Procedure Times (both EMPOWER PG and S-ICD)
 - Fluoro Time (both EMPOWER PG and S-ICD)
 - Implant position (both EMPOWER PG and S-ICD)
 - o Number of EMPOWER PG repositions performed at implant
 - Summary of use of anticoagulation
 - Summary of use of antibiotics
 - o Summary of use of antiplatelets
- Summary of pacing impedance and sensing amplitude at protocol-required follow ups
- Summary of ventricular tachycardia (VT)/ ventricular fibrillation (VF) S-ICD conversion and sensing interaction testing (Implant or Pre-Discharge)
 - Time to shock for induced episodes
 - o Detected rhythm
 - \circ Final Conversion Success Rate successful conversion at \leq 65J shock
 - Summary of Communication Threshold Test at Implant, Pre-Discharge, 1-Month Visit and available Semi-Annual visits
 - Summary of Communication Test results at available Semi-Annual visits
 - Summary of incidence and threshold for Communication Muscle Stimulation at Implant
 - Summary of number of postures with a successful communication test at the 6 Month Visit
 - Summary of EMPOWER PG PCT at protocol-required follow ups
 - Summary of spontaneous treated VT/ VF episodes
 - o Initial Rhythm
 - Method of treatment (ATP, Shock, both)
 - $\circ \quad \mbox{Final Conversion Success} \mbox{Any method}$
 - Time to first therapy (ATP or shock)
 - Summary of communication outcome between the S-ICD and EMPOWER MPS during treated spontaneous episodes, where

communication success will be reported as the number of qualified episodes with ATP delivered over the number of qualified episodes where ATP was requested

- Incidence of syncope related to treated and untreated spontaneous episodes of VT/ VF above the lowest programmed rate cutoff
- Incidence and appropriateness of post-shock demand pacing by the EMPOWER PG
- Summary of Inappropriate Therapy
 - Type of therapy delivered
 - Initial Rhythm
 - Arrythmia acceleration due to ATP delivery
 - Arrythmia induction due to ATP delivery

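### The start rule for time to therapy in spontaneous episodes compares cycle length with the zone cutoff in the wrong direction

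*Protocol*

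**What the plan says.** Table 25-2 in Protocol Section 25.2 defines time to therapy for spontaneous episodes as an interval that starts when the cycle length of the rhythm "is greater or equal to the lowest programmed zone cutoff and measured until the start of delivery of ATP pulses". The interval ends when ATP pulses begin or at the shock marker. The neighbouring entry, for induced episodes, uses a fixed offset of 2000 ms after the last induction artifact and involves no cutoff.

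Elsewhere the protocol treats zone limits as rates:

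- Table 10-9 (Section 10.4.4.2) recommends a conditional shock zone of 180-230 bpm and a shock zone above 230 bpm for primary prevention subjects. Table 10-10 leaves the zone rates to the physician for secondary prevention.
- The footnote to Table 10-9 sets the bound against a pacing rate: "Lower bound of the conditional shock zone should be >3x the Lower Rate Limit (LRL) of EMPOWER".
- The syncope objective in Section 11.2 concerns VT/VF episodes "above the lowest programmed rate cutoff".

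SAP Section 1.3 lists, under treated spontaneous VT/VF episodes, an item reading "Time to first therapy (ATP or shock". It gives no start rule of its own.

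**The concern.** Cycle length shortens as rate rises. A tachycardia enters a zone when its rate reaches the cutoff, that is, when its cycle length falls to the equivalent interval or below. The definition keeps the at-or-above direction that suits a rate but applies it to cycle length. Read literally, the condition already holds in the baseline rhythm and stops holding when the arrhythmia enters the zone.

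What is at stake is a descriptive timing summary. If the rule were applied as printed, the interval would not run from zone entry to first therapy. If it were silently corrected in use, the rule actually applied would differ from the one in the protocol.

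**Working it through.** There is no plan figure to reproduce, since no sample size, power or alpha is involved. The check is one of direction.

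**Inputs.** The start rule comes from Table 25-2. The zone bounds of 180 and 230 bpm come from Table 10-9. The heart rates in the table below are illustrative.

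**Formula.** Cycle length in ms = 60000 / rate in bpm.

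- 180 bpm: 60000 / 180 = 333 ms
- 230 bpm: 60000 / 230 = 261 ms

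**Comparison at a 180 bpm cutoff.**

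| Rate (bpm) | Cycle length (ms) | As written: cycle length ≥ 333 ms | Zone entry: rate ≥ 180 bpm |
|---|---|---|---|
| 60 | 1000 | met | not met |
| 75 | 800 | met | not met |
| 150 | 400 | met | not met |
| 179 | 335 | met | not met |
| 180 | 333 | met | met |
| 181 | 331 | not met | met |
| 200 | 300 | not met | met |
| 230 | 261 | not met | met |
| 250 | 240 | not met | met |

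The two rules agree only at exactly 180 bpm.

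**Any other cutoff.** For a rhythm at rate r and a cutoff c, 60000/r ≥ 60000/c is the same statement as r ≤ c. The reversal therefore does not depend on the 180 bpm value, and it applies equally to zones set at physician discretion under Table 10-10.

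**Comparing the numbers without converting units.** This does not rescue the wording. Setting a cycle length in ms directly against 180 gives 800 ≥ 180 and 300 ≥ 180, so baseline rhythm and VT both qualify. The comparison would fail only for cycle lengths under 180 ms, that is, above 60000 / 180 = 333 bpm.

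**After correction.** With rate ≥ 180 bpm (cycle length ≤ 333 ms), the condition is not met at 60, 75, 150 and 179 bpm and is met from 180 bpm upward. It then marks entry into the lowest zone.

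**The case against.** The strongest reply is that this is a slip that a reader with electrophysiology training would correct on sight. The zones are in bpm, Section 11.2 places episodes above a rate cutoff, and the interval ends at therapy, so the intended direction is clear. The text also names no unit, so strictly it compares an interval with a rate, which is undefined rather than plainly reversed. The intended meaning is indeed easy to recover. That does not make the rule usable as printed: the converted reading is reversed, the unconverted reading separates nothing, and no other text in the two documents supplies a correct start point.

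A second reply is that the SAP does not cite Table 25-2 and uses a slightly different term. That stands, so the link is likely rather than stated. In its favour, Table 25-2 holds the only definition in the documents that covers this interval, and its end points (ATP or shock) match the SAP item.

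A reader might also infer more than the documents support:

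- That this is the principal timing measure for ATP. The SAP lists it as one sub-item of one ancillary summary and gives it no such rank.
- That different readers will use different start points. Nothing in the documents shows this.
- That the error per episode equals all the recording stored before onset. The documents give no stored duration, so neither a figure nor a range can be stated.
- That the Clinical Events Committee's instructions carry the same fault. Section 21.2 refers its procedures to a charter that is not among the documents.

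**Conclusion.** The definition is wrong as written: it reverses the condition for entering the tachycardia zone, at any cutoff. At 180 bpm it is met by a rhythm of 800 ms and not by one of 300 ms. The conclusion rests on the cutoff being a rate, which the zone tables, the Table 10-9 footnote and Section 11.2 all support, and on the reciprocal relation between rate and cycle length.

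The consequence is small. It reaches what is likely the SAP's ancillary time-to-first-therapy summary, and the error in seconds cannot be computed from the documents. No primary or secondary endpoint, hypothesis test, alpha level or power figure is affected. It is a minor correction, but it concerns an operational rule rather than background text.

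**What to change.** In the Table 25-2 entry, make the comparison on the rate of the patient's rhythm, so that the interval starts when that rate is greater than or equal to the lowest programmed zone cutoff. Equivalently, keep cycle length, reverse the inequality to less than or equal to, and compare it with the interval corresponding to that cutoff.

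Change nothing else in the start rule. In particular, do not tie the start to the first beat at or above the cutoff. That would be a new onset rule, because a single early beat could start the clock, and correcting the direction does not require it.

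The cost is one phrase in the definitions table. Device programming, treatment, data collection, sample size and alpha are untouched.
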